6.0 Prospective study

6.1 Study design and overview

This is a multicentre prospective, observational cohort study (**FIGURE 1**). Patients will provide samples and clinical data on 4 different occasions over 12-18 months. For each of the 4 visits individuals will be allocated to be involved in the study either remotely or attend in-person.

3000 individuals will be recruited in total; for 2600 of these patients (remote cohort), their commitment to the study will be entirely remote.

400 individuals (in-person cohort) will be invited to attend a sampling appointment at one of the 4 inperson sampling sites (Birmingham, Southampton, Imperial or Oxford), for each of the 4 study visits. The aim will be to recruit between 120 and 140 individuals per disease/treatment group as detailed in **TABLE 2.**

13 | Page STRAVINSKY Protocol

^{*} This enables assessment of the primary outcome and response to bivalent vaccine. It is highly likely that policy on these licensed treatments will change, in which case we may submit an amendment to individuals receiving SARS-CoV-2 monoclonal Abs.

Informed consent and data collection will predominantly be collected online via a REDCap database. Patients and sites without access to devices or internet will be consented via telephone, the signed paper consent form will then be sent to the participant to counter sign, and they will be asked to post this back to the central study team.

Participants without access to devices to internet will also be offered face to face appointments where the patient can either be supported by the research nurse to complete the online consent form or the participant can sign a paper consent form. If paper consent forms are used, they will be transcribed/scanned into REDCap and the original paper source document will be stored at the recruiting site for the duration of the study. Any case report form (CRF) data collected face to face or via telephone will also be transcribed directly into the database by each local clinical care team. Paper CRF data and consent forms will be transcribed/scanned into REDCap. The original paper documents will be stored at the recruiting site.

There will be a baseline visit which will establish an antibody result at the point of recruitment and establish their medical and COVID-19 infection and vaccination history. There will be 3 further visits that will measure the antibody level prior to booster vaccination, the antibody response at 4-10 weeks post vaccination and then a 4th visit at least 24 weeks after vaccination to examine the longevity of this booster response. Patients can be recruited at any point during their vaccine journey (pre or post vaccine). If patients are recruited after their booster vaccination, they will start at visit 1. Clarification of this route is shown in Appendix 6. Patients will receive their antibody test result.

Booster vaccinations are not being given as part of the study; it is the antibody response to any vaccines that are being given as part of the national vaccination policy that are being examined. If an individual chooses not to have a vaccine they will still be able to take part and we will still measure their antibody levels at equivalent timepoints to those being vaccinated.

Participants will contact the study team or their local clinic team if they test positive for COVID-19 infection, which will enable the study team or local clinical team to complete an online form relating to their illness and to send swabs back to the study to monitor for persistent viral infection.

For participants in the remote cohort (2600) their 4 visits will be all be undertaken remotely but with the option for in person or assisted consent if required. Their contact with the study will be either over the telephone or electronic. They will receive regular electronic updates on the study from the Central Study Team and will have the email and telephone for the Central Study Team if they would like or require individual contact. In addition to this, individuals may receive a telephone call to clarify any history provided by the participant remotely during visits 2-4 or if they suffer from COVID-19 infection. Patients will also be texted their result.

For participants in the in-person cohort (400) they will be enrolled either remotely or in-person and all 4 visits will be in-person to enable an extended sample collection. Contact about the study will then be similar to the remote cohort.

Sponsor: University of Birmingham

Participants will be monitored for COVID-19 infection until the study completes.

FIGURE 1. Visit schedule

3000 participants

Visit 1: BASELINE visit at the time of recruitment (flexible time point but not within the 4 week period after vaccination)

Visit 2: PRE-VACCINATION visit (omitted if less than 12 weeks after visit 1)

Visit 3: PEAK IMMUNE RESPONSE post vaccination (4-10 weeks after vaccine dose)

Visit 4: LONGEVITY of immune response post vaccination (24-36 weeks post vaccine dose)

6.2 Participant identification

Potentially eligible participants (based on underlying conditions) will be identified either through hospital clinics, local hospital clinical databases, localised adverts or through the existing local or ethically approved studies, where patient has given prior consent to be contacted to participate in future studies. They will be contacted either by post, telephone, email, or in-person during routine clinic visits and invited to join the study. They will receive a PIS and copy of the consent form either by post, email or in-person from a member of the study team or clinical team.

Participants whom are not known to local study sites also be able to self-identify for the STRAVINSKY study via the STRAVINSKY webpage and posters and other social media outlets featuring QR codes. Participants will contact the study team through the study email [contact]. The Central Study Team will confirm eligibility. Where possible, we will include individuals that attend the chosen clinical sites to enable access to hospital records, however, for those that self-identify and self-consent in the community (having read and agreed to the participant information sheet) we will request clarification of their clinical history through GP data sources and via access to the National Immunisation and Vaccination System and NHS digital clinical data through their NHS/CHI number.

Informed consent and data collection will be collected online via a REDCap database. Patients and sites without access to devices or internet will be consented via telephone or face to face and the data will be transcribed into the REDCap database. Any case report form (CRF) data collected face to face or via telephone will also be transcribed into the database by each local clinical care team. Copies of all paper CRF data and consent forms must be kept in the site master file for the duration of the study.

6.3 Consent

Once individuals have expressed their interest in the study, they will be sent a link to an online consent form within the REDCap database. Having read the participant information sheet, and are content that they have no further questions, they will sign the consent form. Paper options will also be available as an alternative to be undertaken either remotely and returned by post or be completed

during in-person appointments. It is anticipated that most individuals will consent remotely, however, if an individual is identified when they are attending for a clinical appointment, they will be able to undertake informed consent at the time if this is their preference and it is more convenient for them.

Once an individual has signed the online consent, the Central Study Team will receive an alert that this individual has consented and they will email a pdf copy of the consent form to the individual participant for their personal records and with this email the participant will be informed of their study ID number and given a link to complete a REDCap form to provide information about their underlying condition and their contact details. The local study team will also receive an alert that a patient at their site has consented to arrange for a telephone call to complete the CRF for visit 1. The local study team will use a log to document the time of any telephone call, who it was made by, and the purpose of the call or topics discussed.

If a participant requires support with their consent, chooses not to use electronic consent or has no access to email, informed consent can be undertaken remotely by research nurses or members of the study team, who are on the study delegation log and who are trained in GCP and informed consent. Consent can also be undertaken in-person by these members of the study team. For all individuals there will be the option for remote or in-person consent and this does not pre-determine whether they continue with remote or in-person sampling visits. This ensures as much flexibility as possible for participants (FIGURE 2).

Remote sampling cohort

Identification of participants by research and clinical teams

Self referral

In-person consent

FIGURE 2. Options for remote and in-person consent

6.3.1 Arrangements for individuals who do not have capacity to consent

Some patients may not have the capacity to consent, e.g. individuals in the learning disability group. For these individuals, the clinician will inform the patient's next of kin, personal consultee or legal representative /Welfare Attorney about the study either through telephone call or face to face at the time of recruitment. If the next of kin or personal consultee is not be able to come to the hospital, the research team will send the consultee information sheet and consultee declaration form to them either by post or email. The research team will then obtain the declaration form from the personal consultee or welfare attorney by telephone call witnessed by another member of the research team.

The potential participants will be provided with a simplified poster outlining the study. If they would like to participate, participants' representatives will be given sufficient time to review the PIS and will be given the opportunity to ask questions, once they are able to make an informed decision they will be asked to sign a consent form.

This alternative arrangement will enable vulnerable adults to participate in this study and so inform care for individuals within these disease groups.

6.4 Enrolment

Once the participants are consented, they will be issued a study ID number and added to the REDCap database. Participants will receive an electronic link to input their contact details into the REDCap database. It is necessary for participants to provide contact details to enable dried blood spot (DBS) tests and swabs to be sent to the patient's address, results to be returned by text and their NHS/CHI number and GP's to be able to retrieve vaccine details and other clinical information from primary care records.

When the patient undertakes consent and enrolment, they will provide the following data:

- Demographics (Age, year of birth, height, weight, self-reported ethnicity, sex, NHS number)
- Contact details- Name, address, email address, contact number (preferably mobile to receive antibody result)
- Occupation
- · Name and address of GP
- Which clinical or treatment groups participant self identifies as being part of (SECTION 5.0, also see TABLE 2 on page 13)

All participants will be given contact details of the Central Study Team. Participants will be made aware that they will remain in active follow up and the Central or Local Study Team will contact them during the study either electronically or by telephone call to update them on the study.

Once a participant has consented the REDCap system will alert the Central Study Team and also the local study team that someone from their centre has consented as this will enable the local team to arrange completion of the CRF.

6.5 Visits

Visits will either be all remote, or all in-person for any individual. Unless circumstances arise for practical reasons or patient preference, participants will remain in either the remote or in-person sampling cohorts for each of their 4 visits. A visit checklist is provided in **APPENDIX 2**.

6.5.1 Timing and detail of visits

These visits are arranged around the assumption that there will be a booster campaign, but we acknowledge the study will have to be amended if this is not the case.

Visit 1: Baseline – This is a flexible timepoint depending on recruitment.

At the baseline visit (remote and in-person) patients will be contacted by a research nurse or member of the study team to populate the CRF. The research team member will complete the REDCap online CRF form through this telephone call, with the information detailed below, from the participant. The study team will also be able to confirm clinical details through hospital records, GP records and NHS digital records (e.g. hospital episode statistics and the National Immunisation Management Service) which the patient has consented to. This information will be inputted straight into the REDCap database by the research team. Where this is not possible, for contingency the data will be collated on paper and transcribed onto an electronic CRF on the REDCap secure web application.

The research nurse or clinical team will collect the following data from the hospital records, GP records, National Immunisation or Vaccination System or NHS digital.

Medical conditions / co-morbidities and regular/previous medication as detailed in CRF

 Vaccination history including COVID-19 and other routine vaccinations including influenza or pneumococcal.

Baseline samples will be taken as soon as possible after consent and enrolment into the study. The remote cohort will receive a DBS testing kit in the post and the in-person cohort will provide blood, saliva and nasal samples (described below) during a clinic visit.

Visit 2: This visit is to capture samples just before administration of the booster vaccine.

The purpose of this visit is to measure the lowest antibody level just before vaccination. Ideally this will be within the week prior to the booster vaccination although, patients can be recruited at any point during their vaccine journey (pre or post vaccine).

This visit may be shortly after the Visit 1 depending on when a participant consents. For individuals providing in-person samples the study team can omit this visit if it is less than **12 weeks after Visit 1.** The remote group will continue to complete a dried blood spot sample if they are recruited before September 2023. If recruited after this point this visit can be omitted.

Participants will be asked to complete an electronic REDCap data collection questionnaire or be assisted in this by the research team by telephone if support required. Information collated will include:

- Confirmation of any change in medical and drug history, COVID-19 infection and vaccination history. If the patient answers no to all of these no further action will be taken. If they answer yes they will be asked whether it is a change in their immunosuppressive/chemotherapy/radiotherapy treatment. This will alert the Central and Local Study Teams to check the individual's medical records to confirm this change and if required the patient will be contacted to confirm. If an individual has tested positive for COVID-19 they will be asked to complete a REDCap survey about their illness and where they were treated (see section on testing positive for COVID-19 17.3.1)
- Remote cohort will receive a DBS kit and in-person cohort will provide the same blood, saliva and
 nasal samples as per baseline. For the remote cohort, participants will be asked to logon to
 REDCap to confirm they have sent a sample back to enable sample tracking and their anticipated
 vaccination date (if known). Or participants can email or telephone the study team with this
 information.

Visit 3: All participants will provide a sample **4-10 weeks post vaccination**.

Participants will be asked to complete the same electronic REDCap questionnaire as per visit 2.

Participants will be asked to provide the same samples as per visit 2 depending on whether they are the remote or in-person group.

If a participant does not to receive a booster vaccine (either because they chose not to or suffered a COVID-19 infection at this time), they will be asked will to provide an equivalent sample at any time between November-December 2023 and their clinical record will be reviewed as above.

Visit 4: All participants will provide a sample 24-36 weeks post vaccination.

Visit 4 timelines are flexible and will depend on optimal time according to the planned vaccine schedule. The timing will be at least 24 weeks after the last vaccine but before the next planned vaccine.

Participants will be asked to complete the same electronic REDCap questionnaire as per visit 2.

Participants will be asked to provide the same samples as per visit 2 depending on whether they are the remote or in-person group.

If someone does not want to receive a vaccine during the study (either because they chose not to or suffered a COVID-19 infection at this time), they will be asked will to provide an equivalent sample at any time between October-December 2023 and their clinical record will be reviewed as above.

If someone chooses not to receive a vaccine during the study, they will be asked to provide a blood sample, at any time After April 2024.

Text message reminders and alerts will be sent to patients by the central study team (via FireText as detailed below) prompting them to complete the surveys as timepoints listed.

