6.9 Follow up duration

All participants will remain in the study, for the duration of the study which currently is spring 2025, to monitor for infections and further vaccination.

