8.0 Safety reporting

This is an observational study; we will record only serious adverse events that occur as a result of direct study involvement or death from any cause.

Sponsor: University of Birmingham

The Study Office will report all events assessed to be reportable as serious, unexpected and possibly related to the study procedures (refer to definition below) to the main Research Ethics Committee (REC), and Sponsor within 15 days of the Chief Investigator becoming aware of the event, in accordance with the Sponsor's safety reporting procedures.

Serious Adverse Event

The study acknowledges that multiple serious adverse events are likely to occur during the study due to the natural course of the participants' disease. These are expected events and will not be captured within the study. The study will record only serious adverse events that occur as a result of direct study involvement or death from any cause. Note that COVID infection and or hospitalisation for this infection is already captured as part of the study procedures.

- Related Event
 - An event which resulted from the administration of any of the study procedures.
- Unexpected Adverse Event (UAE)
 - The type of event that is not listed in the protocol as an expected occurrence.
- Unexpected and Related Event
 - An event which meets the definition of both an Unexpected Event and a Related Event.

Expected related events that do not need to be reported as an AE / SAE include:

- 1. Contact bleeding from the nose following a swab, that stops within 15 minutes
- 2. AEs are commonly encountered in participants having blood tests however blood testing is usually well tolerated. The most common adverse event is an individual feeling faint, during phlebotomy. Facilities, including a bed on which to lie, will be available to mitigate this if required. Sometimes there is bruising at the puncture site. This is a common adverse event and so will not be recorded or reported.

Reporting Procedure

Events defined as serious and related to the study or death from any cause require reporting as an SAE and should be reported on an online SAE Form. When completing the form, the Principal Investigator or named delegate will be asked to define the causality and the severity of the SAE. On becoming aware that a participant has experienced an SAE, the Investigator (or delegate) must complete, date and sign an SAE Form.

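### COVID-19 hospitalisation is treated as already captured, but every written route to it starts with the participant, and no admissions or vital-status search is scheduled for all participants

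*Protocol*

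**What the plan says.** Section 8.0 limits safety recording: "The study will record only serious adverse events that occur as a result of direct study involvement or death from any cause". It then explains why COVID-19 events are not collected this way: "Note that COVID infection and or hospitalisation for this infection is already captured as part of the study procedures".

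The procedures it relies on are these:

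- **Section 6.1:** "Participants will contact the study team or their local clinic team if they test positive for COVID-19 infection". The study or local team then completes a form on the illness.
- **Section 6.7 and Appendix 2:** a survey link stays open throughout the study, and swabs are sent once a positive test is reported. Appendix 2 makes the participant responsible for reporting infection in both cohorts.
- **Section 6.5.1, Visit 2:** a questionnaire asks about changes in medical and drug history, COVID-19 infection and vaccination. "If the patient answers no to all of these no further action will be taken". After a positive answer, the records check is written for a change in immunosuppressive, chemotherapy or radiotherapy treatment. Illness details and place of treatment come from a survey that the participant fills in. For Visits 3 and 4: "Participants will be asked to complete the same electronic REDCap questionnaire as per visit 2".

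Under Visit 1, the same section lets the team confirm clinical details from hospital and GP records and "NHS digital records (e.g. hospital episode statistics and the National Immunisation Management Service) which the patient has consented to". Section 6.9 states: "All participants will remain in the study, for the duration of the study which currently is spring 2025, to monitor for infections".

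**The concern.** Disease severity is part of the primary objective (section 4.2). Appendix 3 models a severe composite that includes hospitalisation and death, and treats death as the competing event in the time-to-infection analysis. These outcomes need a source that still works when the participant is in hospital, lacks capacity or has died. The written procedures supply none for the cohort as a whole.

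There are two separate gaps:

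- **A mistaken or forgotten negative answer** at Visits 2 to 4 is never checked against records.
- **No answer at all** prompts only text, and no look-up.

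Appendix 3 analyses complete data without imputation and does not say how silence is coded. If silence counts as no event, the participant is misclassified. If it counts as missing, the participant drops out of the analysis. These are different errors, and the plan leaves both open.

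**Working it through.** **1. Which written routes work without the participant?**

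| Route | Section | Started by | Covers |
|---|---|---|---|
| Call to study or local team | 6.1, App. 2 | Participant | All |
| Survey link, swab kit | 6.7 | Participant | All |
| Questionnaire, Visits 2–4 | 6.5.1 | Participant's answer | All who respond |
| Records check after a positive answer | 6.5.1 | Participant's answer | Treatment change |
| Clinical record review | 6.5.1 | Team | Not boosted only |
| SAE form for a death | 8.0 | Team, on becoming aware | All, if known |

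Only the last two do not start with the participant. The record review leaves out booster recipients, on whom the primary analysis rests. The SAE route needs awareness that nothing scheduled provides. The remote cohort is 2600/3000 = 87% of the study, and Appendix 2 allows for self-referred people who are registered at no participating site.

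**2. The plan's own power figure.** Inputs from Appendix 3: 750 low/no responders, 2250 normal responders, 90% power, two-sided 5%, and a conservative rate of 50%.

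Power = Φ[(d − 1.96·SE0)/SE1], where SE0 uses the pooled proportion and SE1 the separate ones. For 56.81% vs 50%:

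- pooled proportion = (750×0.5681 + 2250×0.5)/3000 = 0.5170
- SE0 = √[0.5170×0.4830×(1/750 + 1/2250)] = 0.02107
- SE1 = √[0.5681×0.4319/750 + 0.25/2250] = 0.02093
- (0.0681 − 1.96×0.02107)/0.02093 = 1.28, so power is 90%

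The detectable difference is 6.8 points. The odds ratio is 1.32, and ln(OR)·√3/π = 0.151. This agrees with the plan's claim of under 10% and with its lower bound of 0.15. The other bounds cannot be checked, because the rates behind them are not given.

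**3. Illustration of under-capture of hospitalisation alone.** The protocol states no capture rate and no hospitalisation rate, so all rates here are assumptions. Take 2% in normal responders and 4.34% in low responders, the difference detectable with 90% power. Observed risk = true risk × capture, with missed events counted as no event. OR = [p1/(1−p1)]/[p0/(1−p0)]. Expected events = 750·p1 + 2250·p0.

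| Capture low / normal | Observed risks | Events | OR | Power |
|---|---|---|---|---|
| 100% / 100% | 4.34% / 2.00% | 77.6 | 2.22 | 90% |
| 80% / 80% | 3.47% / 1.60% | 62.0 | 2.21 | 83% |
| 70% / 70% | 3.04% / 1.40% | 54.3 | about 2.2 | 79% |
| 70% / 90% | 3.04% / 1.80% | 63.3 | 1.71 | 53% |
| 60% / 90% | 2.60% / 1.80% | 60.0 | 1.46 | 29% |

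Repeating the 70%/90% row with a 1% or 5% base rate, each set against its own detectable difference, gives power of 63% or 33%.

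With a larger assumed effect, 6% vs 2%, the true OR is (0.06/0.94)/(0.02/0.98) = 3.13, with 45 + 45 = 90 events. At 70%/90% capture the OR is (0.042/0.958)/(0.018/0.982) = 2.39, with 31.5 + 40.5 = 72 events.

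**The case against.** A reader might infer that COVID-19 deaths, like admissions, are left out of SAE reporting. They are not: "Events defined as serious and related to the study or death from any cause require reporting as an SAE". The sentence about existing capture names infection and hospitalisation only.

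A reader might also infer that the sickest participants are the ones missed. The documents do not show this. The quoted sentence concerns people who respond and report nothing. Someone admitted who recovers can answer positively and is then asked where they were treated. Section 6.7 also covers infection found by swab in hospital.

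Other text points the same way. Section 6.4 promises active follow-up with contact by telephone or electronically. Section 6.1 allows calls to clarify history. Section 6.2 gives access to GP and NHS Digital data for self-referred people. Operational detail may also sit in documents not shown. All of this stands, but it describes access and general contact. None of it schedules an outcome search.

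On impact, Appendix 3 makes infection the primary outcome and calls hospitalisation secondary. Its severe composite also counts infection itself, so a missed admission changes that composite only if the infection was missed too. The odds ratios above apply to hospitalisation alone. The Appendix 3 infection window ends at Visit 4, so the lack of a scheduled visit afterwards affects the monitoring promised in section 6.9, not the primary analysis. These points stand and limit the consequence.

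**Conclusion.** The concern holds in a limited form. Section 8.0 rests on capture that the protocol sets out only as participant-triggered, and no search for COVID-19 admissions or vital status is scheduled for all participants. Admitted or deceased participants are at risk of being missed for infection, for hospitalisation and for death as the competing event.

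The size is unknown, because the protocol gives no capture rate. If under-capture is equal in the two antibody groups, the cost is mainly events and power: 90% falls to 83% or 79% at 80% or 70% capture, and the odds ratio hardly moves. Attenuation towards the null needs lower capture in low responders. That is plausible if they are frailer, but it is an assumption, and the documents do not support stating it as fact. This is a cheap improvement to outcome ascertainment, and the study's validity does not depend on it alone.

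**What to change.** - **Sections 6.5.1 and 6.9, Appendix 2:** add a search of the already-consented hospital, GP and hospital episode records, by NHS/CHI number, for COVID-19 admissions and vital status. Do it for every participant at the Visit 4 time point and again at close of follow-up, whatever the questionnaire answer and also where none was returned.
- **Appendix 3:** derive hospitalisation and death from this search plus self-report.
- **Section 8.0:** make the statement about existing capture refer to this search.
- **Section 6.5.1:** correct the pointer to a section 17.3.1 on positive tests. Section 17 is patient and public involvement, and the infection procedure is in 6.7.

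The cost is data-request work and some lag in linked data. Two passes over 3000 people make 2 × 3000 = 6000 checks if done one by one. No new visit, sample or procedure is needed, and the record sources are already covered by consent.
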